#### 4.0 **OBJECTIVES**

#### 4.1 **Primary Objectives**

The primary objective of this study is to characterize the safety and tolerability of TAK-020 following single and multiple oral doses in healthy subjects.

#### 4.2 Secondary Objectives

The secondary objectives of this study are:

- To characterize the pharmacokinetics (PK) of TAK-020 following single and multiple oral doses.
- To characterize the pharmacodynamics (PD) of TAK-020 following single and multiple oral doses.

#### 4.3 Additional Objectives

Not applicable.

#### 4.4 Study Design

This is a phase 1, randomized, double-blind, placebo-controlled, single and multiple-dose study in healthy volunteers. The study is comprised of 2 parts, each with multiple cohorts and is presented in the Study Schematic below. The study population for each part will be composed of healthy subjects aged 18 to 55 years, inclusive, who weigh at least 45 kg, and have a body mass index (BMI) between 18 and 32 kg/m^2, inclusive, at Screening and Day -1.

SRD=single-rising dose, MRD=multiple-rising dose.

Part 1: Single-Rising Dose (SRD)

This part will comprise a maximum of 9 cohorts. Each cohort will comprise of 8 randomized subjects, with 6 receiving TAK-020 and 2 receiving placebo in the fasted state. Sentinel dosing will be used for Cohort 1 with only 2 subjects dosed on the morning of Day 1 (1 receiving TAK-020 and 1 receiving placebo). The remaining subjects will be dosed following agreement with the investigator and Takeda after reviewing 24-hour postdose safety (adverse events [AEs], vital signs, 12-lead electrocardiograms [ECGs]) and tolerability data. Sentinel dosing will not be necessary for other cohorts provided that exposure is observed in  $\geq$ 4 subjects receiving active

TAK-020-1001	Page 8 of 31
Statistical Analysis Plan Final	22 May 2017

treatment and in agreement with the investigator and Takeda, otherwise sentinel dosing in the subsequent cohort will be required.

TAK-020 will be orally administered as a solution with a starting dose of 0.1 mg for Cohort 1. Dosing for the subsequent cohorts will only occur after review of the safety, tolerability, and minimum 24-hour PK data from the previous cohort. For each dose escalation, exposures may be increased by a maximum of 5-fold for Cohorts 2-4 and a maximum of 2-fold for Cohorts 5-9. Doses may also be decreased as appropriate.

Part 2: Multiple-Rising Dose (MRD)

TAK-020 will be orally administered as a solution. The dose to be used in each cohort will be selected based on data from Part 1 of the study and from the previous cohort in Part 2.

The first cohort for the MRD will receive a dose of 3.75 mg, with a predicted exposure at steady state estimated to be below the no observed adverse effect level (NOAEL) rate (63 ng\*h/mL). The predicted steady state exposure in the first MRD cohort will be approximately 10-fold lower than the highest predicted steady state exposure determined from the SRD data. The MRD will comprise a maximum of 7 cohorts, each cohort with 8 subjects randomized with 6 receiving TAK-020 and 2 receiving placebo. In each successive cohort after the first, the dose increments will increase the predicted exposures by no more than 2-fold. The predicted steady state exposure in the MRD will not exceed the maximum exposure observed in the SRD.

A schematic of the study design is included as Table 4.a. A schedule of assessments is listed in Appendix A.

#### Table 4.aSchematic of Study Design

#### **Study Schematic for Part 1**

Screening	Check-in	Dose	Check-out	Follow-up (a)
Day -28 to -2	Day -1	Day 1	Day 5	Day 14 (±2)

(a) A phone call is planned but individual subjects may be asked to return to the unit at this time if abnormal clinical safety laboratory values are obtained at Check-out or TEAEs have not resolved at Check-out.

#### **Study Schematic for Part 2**

Screening	Check-in	Dose	Washout	Dose	Check-out	Follow-up (a)
Day -28 to -2	Day -1	Day 1	Day 2	Days 3-9	Day 10	Day 17 (±2)

(a) All subjects will return to the unit and complete hematology and serum chemistry tests, vital signs, concomitant medications, and AE assessment.

# 5.0 ANALYSIS ENDPOINTS

# 5.1 **Primary Endpoints**

The primary safety endpoints include the number and percentage of subjects who:

- Experience at least 1 treatment-emergent adverse event (TEAE).
- Meet the Takeda Development Center (TDC) markedly abnormal values (MAV) criteria for safety laboratory tests at least once postdose.
- Meet the TDC MAV criteria for vital sign measurements at least once postdose.
- Meet the TDC MAV criteria for safety ECG parameters at least once postdose.

# 5.2 Secondary Endpoints

The secondary endpoints will be the following PK parameters of TAK-020:

- Maximum observed plasma concentration (Cmax).
- Time to reach  $C_{max}$  ( $t_{max}$ ).
- Area under the plasma concentration-time curve from time 0 to the time of last quantifiable concentration (AUCt).
- Area under the plasma concentration-time curve from time 0 to infinity  $(AUC_{\infty})$ .
- Area under the plasma concentration-time curve during a dosing interval, where tau ( $\tau$ ) is the length of the dosing interval (AUC $\tau$ ).
- t1/2z.
- Apparent clearance after extravascular administration (CL/F).
- Apparent volume of distribution during the terminal phase after extravascular administration (Vz/F).
- Total amount of drug excreted in urine from time 0 to time t (Aet).
- Fraction of drug excreted in urine (fe).
- Renal clearance (CLR).

# **5.3** Exploratory Endpoints

Page 10 of 31 22 May 2017

# 6.0 DETERMINATION OF SAMPLE SIZE

The sample sizes chosen of 8 subjects per cohort (6 active: 2 placebo) in Part 1 and 2 is considered to be sufficient for evaluation of safety, tolerability, PK and the PD of TAK-020 in each cohort. The sample size was not based on statistical power considerations.

# 7.0 METHODS OF ANALYSIS AND PRESENTATION

# 7.1 General Principles

Data for SRD and MRD will be summarized separately over all randomized subjects in each study part. Continuous data will be summarized using descriptive statistics, including the number of subjects (N), mean, standard deviation (SD), median, minimum and maximum. The coefficient of variation (%CV) and geometric mean will be included in the summary of continuous data where indicated. Categorical data will be summarized using the number and percentage of subjects (N[%]) for each category. Missing values will be categorized separately where deemed appropriate and necessary.

In general, the presentation of decimal points will follow the following rules as appropriate: minimum and maximum values will be presented using the same number of decimal places as the recorded data. Means and medians will be presented to 1 more decimal place than the recorded data. SD will be presented to 2 more decimal places than the recorded data. The confidence interval (CI) for a parameter estimate will be presented using the same number of decimal places as the parameter estimate. Percentages will be presented to 1 decimal place (eg, 80.3%). All p-values will be rounded to 3 decimal places. If a p-value is less than 0.001, it will be reported as "<0.001"; if a p-value is greater than 0.999, it will be reported as ">0.999".

All study-related raw data, including derived data, will be presented in data listings.

When no data are available for a table or appendix, an empty page with the title will be produced with suitable text (eg, "There were no subjects with markedly abnormal values of laboratory parameters.").

The Baseline value for a variable is defined as the last observation collected before the first dose of study medication, unless stated otherwise.

Analysis datasets and summary displays will be prepared using SAS version 9.2 or later.

# 7.1.1 Study Definitions

There are no study-specific definitions.

# 7.1.2 Definition of Study Days

Study day will be calculated relative to the date of first dose of study medication for each subject. Study Day 1 is defined as the date on which a subject takes the first dose of study medication, as recorded on the CRF dosing page. Study days prior to the date of first dose of study medication will be calculated as: date of assessment (or event) - date of first dose of study medication. Study days after the date of first dose of study medication will be calculated as: date of study medication will be calculated as: date of study medication will be calculated as: date of first dose of study medication will be calculated as: date of assessment (or event) - date of first dose of study medication + 1.

# 7.1.3 Definition of Study Visit Windows

There will be no visit windowing.

#### 7.1.4 Conventions for Missing Adverse Event Dates

There will be no imputation of incomplete or missing adverse event dates.

#### 7.1.5 Conventions for Missing Concomitant Medication Dates

There will be no imputation of incomplete or missing concomitant medication dates.

#### 7.1.6 Conventions for Missing Data

There will be no imputation of incomplete or missing data.

Plasma concentrations that are below the lower limit of quantification (< LLOQ) will be treated as zero in the summarization of concentration values and derivation of PK parameters.

#### 7.2 Analysis Sets

The following analysis sets will be used for analysis and presentation of the study data:

- All randomized subjects will consist of all subjects who are randomized to a treatment.
- The safety analysis set will consist of all subjects who are randomized to a treatment and receive 1 dose of study drug. Subjects in this analysis set will be used for demographic, baseline characteristics and safety summaries.
- The PK analysis set will consist of all subjects who receive study drug and have at least 1 measurable plasma concentration or amount of drug in the urine. Subjects in this analysis set will be used for all PK summaries and statistical analyses.
- The PD analysis set will consist of all subjects who receive study drug and have at least 1 predose and postdose PD measurement. Subjects in the analysis set will be used for all PD summaries and statistical analyses.

If any subjects are found to be noncompliant in dosing schedule or with incomplete data, a decision will be made on a case-by-case basis as to their inclusion in the analysis but all randomized subjects will be presented in the subject listings.

#### 7.3 Disposition of Subjects

Disposition of all screen failure subjects will be summarized according to the primary reason for screen failure. Additionally, disposition information for screen failures will be listed.

Disposition of all randomized subjects will be summarized by pooled placebo, each TAK-020 dose level and TAK-020 overall. The categories will include:

- Subjects who were randomized, but not treated, if applicable.
- Subjects who completed study drug.
- Subjects who prematurely discontinued study drug.
- Subjects who completed all study visits.

TAK-020-1001	Page 14 of 31
Statistical Analysis Plan Final	22 May 2017

• Subjects who prematurely discontinued study visits.

Primary reasons for discontinuing study drug and/or visits, as entered on the eCRF, will be summarized.

Disposition information for randomized subjects will be listed. The status of the blind for randomized subjects will also be listed. A listing of inclusion/exclusion criteria not met will be provided for randomized subjects who did not meet at least one entrance criterion.

Significant protocol deviations captured on the eCRF will be listed and summarized.

# 7.4 Demographic and Other Baseline Characteristics

Demographic characteristics, including age at informed consent, gender, ethnicity and race will be summarized and listed for screen failure subjects, along with the reason(s) for failure.

Demographic and study baseline characteristics, including age at informed consent, gender, ethnicity, race, baseline height (cm), baseline weight (kg), baseline BMI (kg/m^2), smoking history, alcohol history, caffeine/xanthine history and female reproductive status will be summarized for all subjects in the safety analysis set by pooled placebo, each TAK-020 dose level, TAK-020 overall and total overall. Subjects who identify themselves as belonging to more than 1 race on the eCRF will be classified as multiracial for summarizes and each race selected will be listed. In addition, demographic and baseline characteristics will be summarized for all subjects in the safety analysis set (i.e. SRD and MRD combined) by pooled placebo, TAK-020 and overall.

There will be no inferential analysis of demographic and baseline characteristics.

# 7.5 Medical History and Concurrent Medical Conditions

Medical history is defined as significant conditions or diseases that stopped prior to the signing of informed consent. Concurrent medical conditions are defined as significant conditions that are present or ongoing at or after the signing of informed consent.

Medical history and concurrent medical conditions will be coded using the Medical Dictionary for Regulatory Activities (MedDRA, version 19 or higher) coding system.

Medical history and concurrent medical conditions will be listed separately by site and subject number.

There will be no summary or inferential analysis of medical history and concurrent medical conditions.

#### 7.6 Medication History and Concomitant Medications

Medication history information includes any medication relevant to eligibility criteria stopped at or within 28 days prior to signing of informed consent. Concomitant medications are recorded on the eCRF and include any medications, other than the study drug, taken at any time between informed consent and on or prior to the last dose of study drug.

TAK-020-1001	Page 15 of 31
Statistical Analysis Plan Final	22 May 2017

Medication history and concomitant medications will be coded using the World Health Organization Drug Dictionary (WHODrug) version 01MAR2016 Expanded or higher.

Separate listings for medication history and concomitant medications will be produced by site and subject number.

There will be no summary or inferential analysis of medication history and concomitant medications.

# 7.7 Study Drug Exposure and Compliance

Each subject will be given a single dose in SRD and multiple doses in MRD as per the study design. Since all doses of study medication will be administered during confinement, study drug compliance will not be summarized. Dosing administration as well as study drug concentration data will be provided by subject and visit for SRD and MRD in the listings.

There will be no inferential analysis of study drug exposure.

# 7.8 Efficacy Analysis

Not applicable.

# 7.9 Pharmacokinetic/Pharmacodynamic Analysis

# 7.9.1 Pharmacokinetic Analysis

The schedule of blood samples for PK analysis of TAK-020 is listed in Table 7.a and the schedule of urine samples is listed in Table 7.b.

Plasma concentrations of TAK-020 will be summarized by treatment over each scheduled sampling time using descriptive statistics. The amount of TAK-020 excreted in urine will also be summarized by treatment over each scheduled sampling interval using descriptive statistics. Plasma concentrations and the amount of study drug excreted in urine will be summarized separately for the SRD and MRD portions of the study. Subjects randomized to placebo will not be included in these summarizes but will be listed. Individual plasma concentrations and urine amounts will be listed separately.

# Table 7.aCollection of Blood Samples for Pharmacokinetic AnalysisPart 1 (SRD)

Sample Type	Dosing Day	Time Postdose (hours)				
Plasma	1	Predose (within 30 minutes prior to dosing), and at 0.25, 0.5, 0.75, 1, 2, 3, 4, 6, 8, 10, 12, 16, 24, 36, 48, 72, and 96 hours postdose				

#### Part 2 (MRD)

Sample Type	Dosing Day	Time Postdose (hours)					
Plasma	1	Predose (within 30 minutes prior to dosing), and at 0.25, 0.5, 0.75, 1, 2, 3, 4, 6, 8, 10, 12, 16, 24, 36, and 48 hours postdose					
Plasma	9	Predose (within 30 minutes prior to dosing), and at 0.25, 0.5, 0.75, 1, 2, 3, 4, 6, 8, 10, 12, 16, and 24 hours postdose					

#### Table 7.b Collection of Urine Samples for Pharmacokinetic Analysis

Part 1 (SRD)

Sample Type	Dosing Day	Time Postdose (hours)				
Urine	1	Predose (-12-0), and 0-6, 6-12, 12-24, 24-48, 48-72, 72-96 hour postdose intervals				

# Part 2 (MRD)

Sample Type	Dosing Day	Time Postdose (hours)
Urine	1	Predose (-12-0), and 0-6, 6-12, 12-24 hour postdose intervals
Urine	9	Predose (-12-0), and 0-6, 6-12, 12-24 hour postdose intervals

PK parameters of TAK-020 are listed in Table 7.c and will be determined from the concentration-time profiles for all evaluable subjects.

# Table 7.cPlasma and Urine PK Parameters

The following plasma PK parameters will be determined:

Symbol/Term	Definition			
Plasma/Blood/Serum				
AUC 24	Area under the plasma concentration-time curve from the time 0 to time 24 hours.			
AUC τ	Area under the plasma concentration-time curve during a dosing interval, where tau $(\tau)$ is the length of the dosing interval.			
AUCt	Area under the plasma concentration-time curve from time 0 to time of the last quantifiable concentration.			
$AUC_{\infty}$	Area under the plasma concentration-time curve from time 0 to infinity, calculated as $AUC_{\infty}=AUC_t+C_{last}/\lambda_z$			
R	Accumulation ratio (index) calculated as AUC $\tau$ at steady state/AUC $\infty$ after a single dose.			
$R_{ac(AUC)}$	Accumulation ratio (based on AUC), calculated as $AUC_{\tau}$ at steady state/AUC <math>\tau</math> after a single dose.			
C max	Maximum observed plasma concentration.			
C max,ss	Maximum observed steady-state plasma concentration during a dosing interval.			
CL/F	Apparent clearance after extravascular administration, calculated as =Dose/AUC <math>\infty</math> after a single dose and as Dose/AUC <math>\tau</math> after multiple dosing (at steady state).			
$\lambda_z$	Terminal elimination rate constant, calculated as the negative of the slope of the log-linear regression of the natural logarithm concentration-time curve during the terminal phase.			
t 1/2z	Terminal disposition phase half-life, calculated as $ln(2)/\lambda_z$ .			
t lag	Lag time.			
t max	Time of first occurrence of $C_{max}$ .			
V z /F	Apparent volume of distribution during the terminal phase after extravascular administration, calculated as $(CL/F)/\lambda_z$ .			

The following urine PK parameters of TAK-020 will be determined:

Urine	
Ae t1-t2	Amount of drug excreted in urine from time 1 to time 2, calculated as $C_{ur} \times V_{ur}$ , where $C_{ur}$ is the concentration of drug excreted in urine and $V_{ur}$ is the volume of urine excreted.
Aet	Total amount of drug excreted in urine from time 0 to time t.
Ae τ	Amount of drug excreted in urine during a dosing interval $(\tau)$ at steady state.
f e	Fraction of drug excreted in urine, calculated as (Ae t /dose)×100. Molecular weight adjustment needed for metabolites.
CL R	Renal clearance, calculated as Ae 0-24 /AUC 24 .

Specific or additional PK parameters may be added as appropriate per the Clinical Pharmacology Analysis Plan (CPAP).

PK parameters of TAK-020 will be summarized by treatment using descriptive statistics. In addition, geometric mean and coefficient of variation will be computed for  $C_{max}$  and AUCs. PK

TAK-020-1001	Page 18 of 31
Statistical Analysis Plan Final	22 May 2017

parameters will be summarized separately for the SRD and MRD portions of the study. Individual PK parameters will be listed.

Dose proportionality will be tested for  $C_{max}$  and AUCs of both SRD and MRD using a power model. The power fit will be assumed as described by the following equation:

 $\ln(PK \ Parameter) = \beta_0 + \beta_1 \ln(Dose) + \varepsilon$ 

where  $\beta_0$  is the intercept,  $\beta_1$  is the slope and  $\varepsilon$  is the random error. The 90% CI for  $\beta_1$  will be presented and dose proportionality would be declared when this CI lies entirely within the critical region  $\left(1 + \frac{\ln(0.80)}{\ln(r)}, 1 + \frac{\ln(1.25)}{\ln(r)}\right)$ , where *r* is the ratio of the highest and lowest dose in the study. This criterion implies that the 90% CI for the ratio of the central values of the PK parameter of interest from the highest dose to the lowest dose is contained completely within the bioequivalence range of (0.80, 1.25) [2].

For SRD, the effect of dose on Tmax and  $\lambda z$  will be evaluated using analysis of variance (ANOVA) with treatment as a fixed effect. Means and standard deviations will be presented for all treatments along with a p-value of overall treatment effect. A similar analysis will be completed for Tmax within the MRD portion of the study. This analysis will be done separately for Day 1 and Day 9.

ANOVA will be used to assess time dependency for Part 2 (MRD). The natural log-transformed AUCs and Cmax will be used as response variable and dose level, Day and the interaction of dose level and Day will be fixed factors. Within the frame work of ANOVA, 90% CIs for the ratio of AUCs and Cmax central values between Day 9 and Day 1 will be presented.

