# **Dose and Dose Regimen**

The starting dose of 0.1 mg was based on both the Food and Drug Administration (FDA) guidance [7] and PK/PD modeling which predicted 20% BTK occupancy, which is considered to represent a minimum anticipated biological effect level.

Currently doses of 0.1, 0.5, 2.5, 4.4, 8.8, 17.5, 35, 70, and 105 mg have been tested in the SRD and 3.75, 5.75, 13 and 25 mg in the MRD and were shown to be safe and well tolerated. Draft PK data are summarized in Table 6.b and Table 6.c for the SRD and MRD, respectively.

Cohort (Dose)	C max (ng/mL)	T max * (hr)	AUC 24 (ng*h/mL)	AUC t (ng*h/mL)	$AUC_{\infty}$ (ng*h/mL)	Half-life (hr)

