#### 8.1.3 Dose and Regimen

In Cohorts 1 to 9, doses of 0.1, 0.5, 2.5, 4.4, 8.8, 17.5, 35, 70, and 105 mg have been evaluated. The investigator or investigator's designee will instruct the subject on dosing procedures. All dosing will occur while subjects are in the clinic under the supervision of the PI or designee. On dosing days, subjects will be given TAK-020 or placebo oral solution. A separate pharmacy manual will describe how each dose regimen will be formulated.

Study drug will be administered at the same time on each dosing day (approximately 0800 hours). After initial administration, the dosing bottle shall be rinsed twice with about half the volume of the bottle with water. The rinse will be administered to the subject. The exact time of dose will be recorded in the source documents and on the appropriate eCRF.

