# 13.1.3.2 PK Parameters

Descriptive statistics [N, arithmetic mean, SD, median, minimum, maximum and percent coefficient of variation (%CV)] will be used to summarize the plasma PK parameters for TAK-020 by dose level and population. In addition, geometric mean and coefficient of variation will be computed for  $C_{max}$  and AUCs. All PK parameter data will be listed.

Power model will be used to assess dose proportionality for Cmax and AUC in each part.

The power model will be assumed as described by the following equation:

$$\log(PKParameter) = \beta_0 + \beta_1 \log(Dose) + \varepsilon$$

Where  $\beta_0$  is the intercept,  $\beta_1$  is the slope and  $\varepsilon$  is the random error.

The 90% confidence interval (CI) of the slope estimate will be presented. The dose proportionality would be declared when the 90% CI for  $\beta$ 1 lies entirely within the critical region:

$$\left(1 + \frac{\ln(0.80)}{\ln(r)}, 1 + \frac{\ln(1.25)}{\ln(r)}\right),$$

where r is the ratio of the highest and the lowest dose in this study. This criterion implies that the 90% CI for the ratio of the central values of PK parameter of interest from the highest dose to the lowest dose is contained completely within the bioequivalence range of (0.80, 1.25).

Analysis of variance (ANOVA) will be performed for  $T_{max}$  and  $\lambda_z$  after a single or multiple dose administration to evaluate the effect of dose on  $T_{max}$  for SRD and MRD parts and  $\lambda_z$  for SRD part.

ANOVA will be used to assess time dependency for Part 2 (MRD). The natural log-transformed AUCs and  $C_{max}$  will be used as response variable and dose level, Day and the interaction of dose level and Day will be fixed factors. Within the frame work of ANOVA, 90% CIs for the ratio of AUCs and  $C_{max}$  central values between Days 9 and 1 will be presented.

Detailed analysis methodologies will be presented in SAP as necessary.

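### The dose-proportionality rule takes one dose ratio r from the whole study (105/0.1 = 1050), so as written the Part 2 slope limits are 2.0 to 3.7 times narrower than the stated 0.80 to 1.25 criterion requires

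*SAP*

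**What the plan says.** The power model is to be fitted part by part. Protocol 13.1.3.2 applies it to Cmax "and AUC in each part", and SAP 7.9.1 covers Cmax and "AUCs of both SRD and MRD using a power model". The printed model has an intercept and one slope on log dose, with no term for study part.

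Dose proportionality is declared when the 90% CI for the slope lies inside 1 + ln(0.80)/ln(r) to 1 + ln(1.25)/ln(r). Each document defines r once: in the SAP it "is the ratio of the highest and lowest dose in the study", and the protocol has "where r is the ratio of the highest and the lowest dose in this study". Neither gives an r for each part.

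Both then explain the rule. The SAP sentence begins "This criterion implies that the 90% CI for the ratio of the central values of the PK parameter" and goes on to say that this CI, comparing the highest with the lowest dose, falls inside 0.80 to 1.25.

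On doses, Protocol 8.1.3 states for Part 1 that "doses of 0.1, 0.5, 2.5, 4.4, 8.8, 17.5, 35, 70, and 105 mg have been evaluated". Section 6.2 lists "3.75, 5.75, 13 and 25 mg in the MRD". Figure 6.b leaves MRD Cohorts 5 to 7 to be determined.

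**The concern.** The slope limits correspond to 0.80 to 1.25 only if r is the dose range of the data in the fit. The lowest and highest doses in the study are both Part 1 doses. The lowest listed MRD dose is 3.75/0.1 = 37.5 times the lowest SRD dose, so the MRD fit cannot span the study-wide range, whatever its top dose turns out to be. The definition of r and the sentence explaining it therefore cannot both be true for Part 2.

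At stake is the Part 2 statement on proportionality of Cmax and AUC. Two programmers could each cite the SAP, use a different r, and report opposite conclusions from the same slope and CI.

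A second, smaller fault lies in the explaining sentence itself. It speaks of the ratio of central values without saying that they are dose-normalised, and so is untrue as printed for both parts.

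**Working it through.** **Inputs.** The rule is from SAP 7.9.1 and Protocol 13.1.3.2. SRD doses run from 0.1 to 105 mg (Protocol 8.1.3), and MRD doses so far are 3.75, 5.75, 13 and 25 mg (Protocol 6.2), with 6 active subjects per cohort. MRD top doses above 25 mg are assumptions; the upper one, about 122 mg, is the highest dose named in the Study Summary. The between-subject CVs are also assumptions, because the PK values in Tables 6.b and 6.c are not shown in the public text.

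**Step 1: reproduce the stated criterion.** Under the power model, the dose-normalised ratio of central values between two doses a factor R apart is R^(slope − 1). At the limits, slope − 1 = ±ln(1.25)/ln(r), since ln(0.80) = −ln(1.25). The implied ratio limits are therefore 1.25^(±ln R/ln r), which equal 0.80 and 1.25 only when R = r.

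For Part 1, R = r = 1050, ln(1050) = 6.957 and the half-width is 0.2231/6.957 = 0.0321. The region is 0.968 to 1.032, and the plan's statement reproduces.

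**Step 2: the same rule in Part 2.** The narrowing factor is ln(1050)/ln(r for MRD). The last column is the dose-normalised range that r = 1050 actually enforces over the MRD doses.

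| MRD top dose | r for MRD | ln r | Limits with own r | Narrowing with r = 1050 | Range enforced with r = 1050 |
|---|---|---|---|---|---|
| 25 mg (listed) | 6.667 | 1.897 | 0.882 to 1.118 | 3.67 | 0.941 to 1.063 |
| 50 mg (assumed) | 13.33 | 2.590 | 0.914 to 1.086 | 2.69 | 0.920 to 1.087 |
| 105 mg (assumed) | 28.00 | 3.332 | 0.933 to 1.067 | 2.09 | 0.899 to 1.113 |
| 122 mg (assumed) | 32.53 | 3.482 | 0.936 to 1.064 | 2.00 | 0.894 to 1.118 |

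If 122 mg were given, it would also become the study's top dose. Then r = 1220, ln(1220) = 7.107, and the factor is 7.107/3.482 = 2.04.

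**Step 3: the missing word.** At a true slope of exactly 1, the ratio of central values without dose normalisation equals r: 1050 in Part 1 and 6.67 in Part 2 (listed doses). Neither is between 0.80 and 1.25.

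**Step 4: effect on the declaration.** The SE of the slope is σ/√Sxx, where σ = √ln(1 + CV²) and Sxx is the sum of squares of ln(dose). For the four listed cohorts Sxx = 12.87 with 22 df. At CV 15%, σ = 0.149, the SE is 0.149/3.588 = 0.0416, and the 90% CI half-width is typically 1.717 × 0.0416 = 0.071. This fits inside ±0.118 but not inside ±0.032, even if the estimate is exactly 1.

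The table gives the probability of declaring proportionality when the true slope is 1, from 2,000,000 simulated slopes and SEs per case. Each cell is r = 1050 versus the part's own r.

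| MRD cohorts | CV 10% | CV 15% | CV 20% | CV 30% |
|---|---|---|---|---|
| Four, as listed (Sxx 12.87, 22 df) | 0.1% vs 99% | <0.1% vs 73% | <0.1% vs 33% | <0.1% vs 1.5% |
| Five, fifth assumed 50 mg (Sxx 26.72, 28 df) | 6% vs 99% | <0.1% vs about 80% | <0.1% vs 42% | <0.1% vs 2.3% |
| Seven, last three assumed 50, 75 and 105 mg (Sxx 59.06, 40 df) | 57% vs >99% | 5% vs 92% | 0.04% vs 64% | <0.1% vs 9.6% |

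At CV 25%, the own-r figures are 9%, 13% and 32%, against less than 0.1% with r = 1050.

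**The case against.** The strongest reply is that the intent is clear. The model is applied by part, the target of 0.80 to 1.25 is stated, and only an MRD-specific r is consistent with that target in Part 2. Protocol 6.2 even refers loosely to Part 2 as a study. On this view the point is a clarification and no wrong analysis has been shown. The intent is plausible, but neither document states it. Both describe the study as having two parts, and the SAP speaks of SRD and MRD as portions of the study, so the literal reading is also the natural one.

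The other objections stand as limits on size:

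- The factor depends on MRD doses not yet fixed: 3.7 applies if MRD stops at 25 mg, and 2.0 needs about 122 mg.
- The large contrasts need a CV of about 10 to 20%, which the documents neither support nor exclude. Low oral bioavailability in animals, likely P-gp transport and several CYP routes (Protocol 4.1) make very low variability less plausible. From about 30% upward, proportionality is rarely declared with either r.
- The error is conservative. It can withhold a Part 2 declaration that the stated criterion would allow, but it cannot create one that the criterion would refuse. The 90% CI for the slope is reported either way, so a reader could apply another r.
- The missing word changes no calculation.

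**Conclusion.** The concern holds. As written, r = 1050 applies to both parts, and in Part 2 it contradicts the criterion that the plan says it implements. The slope region is 3.7 times too narrow for the listed MRD doses, falling to 2.0 times if the top dose reached about 122 mg. The regions follow exactly from the listed doses; the values for higher MRD doses, and every declaration probability, rest on the stated assumptions.

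The practical effect is largest at CVs of about 10 to 25%, where Part 2 data that are exactly proportional would in most of these scenarios fail a test that they could pass with the correct r. Part 1 is unaffected, and neither the primary safety endpoints nor dose escalation uses the rule. This should be corrected because it is a stated decision threshold that is wrong as written, although it bears only on a secondary PK conclusion. The omission of *dose-normalised* is a separate and lesser error.

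**What to change.** In SAP 7.9.1 and Protocol 13.1.3.2:

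1. Define r as the ratio of the highest to the lowest dose among the subjects in the fitted model, separately for SRD and for MRD (and for each MRD day fitted).
2. Insert *dose-normalised* before the ratio of central values in the sentence that explains the criterion.

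The cost is one phrase and one word in each document. Data collection, sample size and the Part 1 limits do not change. The wording should be settled before the Part 2 PK results are seen, so that r is not chosen with the slope in view.
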